1.0 Study Summary*

The diagnosis of necrotizing enterocolitis (NEC) – an acute and life-threatening intestinal disease that affects 5-10% of infants – can be challenging. Traditionally, neonatologists rely on abdominal radiographs (AXR) to evaluate infants with concern for NEC. In recent years, bowel ultrasound (BUS) has been proposed as a helpful adjunct to AXR for NEC evaluation. In centers where BUS expertise is available, clinicians now have the option of using BUS in addition to AXR in their diagnostic evaluation for NEC. However, significant variability remains on whether neonatologists would use or not use BUS in this clinical setting. An important reason for this variability is the lack of evidence regarding whether BUS improves patient outcomes or not. Additionally, BUS expertise generally is available only in highly specialized children's hospitals. Thus, in centers with limited BUS availability, AXR remains the standard imaging modality for NEC. ***The lack of rigorous and robust clinical trials conducted in diverse NICU settings is an important gap in knowledge that needs to be addressed before the routine use of add-on BUS for NEC evaluation.***

To help address these limitations, we propose to conduct comparative effectiveness research to evaluate the benefits of add-on BUS on patient outcomes. Our study design will be a pragmatic randomized clinical trial (RCT) of AXR versus AXR + BUS in infants with suspected NEC. We propose to conduct this study in two diverse sites. The first site will be the level IV NICU of Children's Mercy Kansas City (CMKC), which already has expertise in BUS for NEC. The second site will be the level III NICU of University of Kansas Medical Center (KUMC), an adult hospital with less experience in BUS. The rationale for this study is that infants at high risk for NEC are cared for in diverse settings including level III NICUs in adult hospitals that have little experience in using BUS to evaluate NEC. Our study has two specific aims.

Specific aim #1: To determine the impact of add-on BUS for NEC evaluation on patient outcomes in two different NICU settings. We hypothesize that adding BUS to NEC evaluation changes differential diagnosis, therapy plan and patient outcomes.

Specific aim #2: To determine the capability of implementing BUS for NEC evaluation in a level III NICU within an adult hospital. We hypothesize that BUS timeliness, quality, and inter-rater reliability are comparable between level III and IV NICUs.

The addition of BUS to the diagnostic repertoire of infants with suspected NEC is an important contribution to neonatology. Before widespread adoption can be realized, however, strong evidence is needed to determine whether the addition of BUS would lead to actual clinical benefits, including in level III NICUs in adult hospitals. We anticipate that our study will help address this critical gap in knowledge and provide important insights as to the safe and effective use of BUS for NEC.

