2.0 Objectives*

2.1 Purpose, specific aims or objectives:

The overall objective of our study is to determine the clinical usefulness of BUS for NEC evaluation in diverse NICU settings. We plan to accomplish this overall objective by completing the following specific aims:

Specific aim #1: Determine the impact of add-on BUS for NEC evaluation on patient outcomes in two different NICU settings.

Specific aim #2: Determine the capability of implementing BUS for NEC evaluation in a level III NICU within an adult hospital.

2.2 Hypothesis:

Our hypothesis is that the addition of BUS to AXR can favorably change differential diagnosis, therapy plan, and patient outcomes of infants with suspected NEC; and that this beneficial impact extends to less specialized centers with little prior experience with BUS for NEC evaluation.

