10.9 Blood and Other Specimen Collection: NA

11.0 Surveys and Psychometric Testing:

- We will conduct two surveys to determine change in clinician's diagnostic and therapeutic thinking. The first survey (post-AXR survey), applicable to all infants, will be conducted after AXR is performed. The second survey (post-BUS survey), applicable only to infants randomized to AXR + BUS, will be conducted after BUS is performed. Surveys will be answered by the neonatologist taking care of the infants using a 5-point Likert scale from "not at all likely" to "extremely likely".

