26.0 Data Collection*

26.1 The study will collect baseline clinical characteristics, lab test results, AXR and BUS results, clinical diagnosis, treatment data, and survey results.

- Clinical characteristics: gestational age at birth, weight at birth, sex, race/ethnicity, age at time of NEC concern,
- Lab test results: complete blood cell count (CBC), C-reactive protein (CRP), blood culture
- AXR and BUS results: time of order input in the chart, time of image acquisition, time of reporting, text of report and interpretation by radiologist
- Clinical diagnosis: NEC, no NEC, food protein-induced enterocolitis, clinical sepsis, other diagnosis

- Treatment data: medical treatment of NEC including days of bowel rest, days to full enteral feeds, days on antibiotics; surgical treatment of NEC including peritoneal drainage or exploratory laparotomy
- Survey results: post-AXR survey and post-BUS survey by neonatologists

26.2 Data will be obtained from the electronic medical record and surveys/questionnaires.

26.3 Sensitive Data: We will not be collecting or accessing sensitive data.

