28.0 Statistical Analysis*

28.1 We will use two-tailed McNemar's test with paired measures to analyze differences in diagnostic thinking efficacy and therapeutic efficacy from pre- and post-BUS surveys. Comparison of duration of antibiotics, bowel rest, and days to full enteral feeds will be performed using Student's t-test. Kaplan-Meier curve will be used to analyze time to full feeds between the 2 groups, censoring for death, discharge/transfer out of the hospital, or 30 days following initial NEC concern. Analyses of patient outcomes (duration of bowel rest, duration of antibiotics, time to full feeds) will follow the intention-to-treat principle, with statistical significance set at a P value of < 0.05.

28.2 We will use t-test to analyze differences in mean time of BUS image acquisition and reporting. Chi-square test will be used to compare differences in proportion of BUS studies that were performed and reported per standardized protocol. Inter-rater reliability for BUS studies will be assessed by Cohen's kappa statistics.

28.3 Sample size was calculated based on our pilot study which demonstrated a mean \pm SD of duration to full enteral feeds of 16 ± 9 days per episode of NEC concern. Using this information, we generated Table 1, which shows sample sizes for a range of possible means and standard deviations, with significance level of 0.05 and 80% power. For a 1-year study with 67 to 81 distinct episodes, for an SD of +8 days, we anticipate having sufficient sample size to detect a 5- to 6-day difference in mean duration to full feeds (highlighted in gray in Table 1).

Difference of means between groups	Expected Standard Deviation		
	± 8	± 9	± 10
4 days	126	160	198
5 days	81	102	126
6 days	56	72	88

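### Aim 1 hypothesises that adding BUS changes diagnosis, but the plan examines diagnosis only within the AXR + BUS arm, so it yields no randomised evidence on that claim

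*Combined protocol and SAP*

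**What the plan says.** The hypothesis appears twice. Section 1.0, Specific aim #1: "We hypothesize that adding BUS to NEC evaluation changes differential diagnosis, therapy plan and patient outcomes". Section 2.2 gives it a direction: "the addition of BUS to AXR can favorably change differential diagnosis, therapy plan, and patient outcomes of infants with suspected NEC".

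Section 26.1 lists among the data to be collected: "Clinical diagnosis: NEC, no NEC, food protein-induced enterocolitis, clinical sepsis, other diagnosis". It does not restrict this item to one arm.

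Section 28.1 has one analysis that touches diagnosis, a two-tailed McNemar test with paired measures "to analyze differences in diagnostic thinking efficacy and therapeutic efficacy from pre- and post-BUS surveys". Section 11.0 says who supplies the pairs. On the first survey: "The first survey (post-AXR survey), applicable to all infants, will be conducted after AXR is performed". The second is "applicable only to infants randomized to AXR + BUS, will be conducted after BUS is performed".

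The outcomes that 28.1 compares between arms are durations: "Analyses of patient outcomes (duration of bowel rest, duration of antibiotics, time to full feeds) will follow the intention-to-treat principle". Diagnosis is not among them. Section 28.2 covers the timing, quality and inter-rater reliability of BUS and does not mention diagnosis either.

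**The concern.** Change in diagnosis is the first effect named in Aim 1, and the trial allocates infants to two imaging strategies so that such effects can be compared between arms. As planned, a statement that BUS changes diagnosis would rest on uncontrolled data. A clinician's view may shift between the two surveys because of BUS, or because laboratory results arrive and the clinical course becomes clearer. The AXR arm has no second survey, so this drift cannot be measured.

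The gap also limits how the duration results can be explained. Section 10.8 leaves treatment, including the length of bowel rest and of antibiotics, to the treating neonatologist's judgement, so durations can follow the label given. A shorter mean in the AXR + BUS arm could come from fewer infants being called NEC, or from shorter treatment of infants with the same label. A strategy that labels more infants as NEC would not be visible in the planned results.

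**Working it through.** **1. Is there any between-arm analysis of diagnosis?** Set side by side:

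| Item | Where | AXR arm | AXR + BUS arm | Analysis in section 28 |
|---|---|---|---|---|
| Post-AXR survey | 11.0 | yes | yes | first half of the McNemar pair |
| Post-BUS survey | 11.0 | no | yes | second half of the McNemar pair |
| Clinical diagnosis | 26.1 | yes | yes | none |
| Bowel rest, antibiotics, time to full feeds | 26.1 | yes | yes | between arms, intention-to-treat |

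A complete survey pair exists only in the AXR + BUS arm. Comparing the post-AXR survey by arm would not fill the gap, because that survey is the pre-BUS measurement in the pair.

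**2. The plan's own sizing.** Table 1 in 28.3 concerns days to full feeds only. Total N = 4 × (1.960 + 0.842)² × SD² / difference². For 5 days and SD 8 this is 4 × 7.849 × 64 / 25 = 80.4, which rounds up to the stated 81. The table reproduces as totals over both arms: rounding up per arm matches the other eight cells exactly and gives 82 in this one. Nothing in it sizes a comparison of diagnosis.

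**3. Precision of a by-arm diagnosis comparison.** Inputs: 80 infants (target in Addendum B), or 200 (goal in 8.0), allocated 1:1 (assumed, as the ratio is not stated). The documents give no NEC share, so p = 0.2 to 0.5 is assumed, equal in both arms. Half-width of the 95% CI = 1.96 × √(2p(1 − p)/n), with n per arm:

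| p | n = 40 | n = 100 |
|---|---|---|
| 0.2 | 1.96 × √(0.32/40) = 0.175 | 1.96 × √(0.32/100) = 0.111 |
| 0.3 | 1.96 × √(0.42/40) = 0.201 | 1.96 × √(0.42/100) = 0.127 |
| 0.5 | 1.96 × √(0.50/40) = 0.219 | 1.96 × √(0.50/100) = 0.139 |

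That is 18-22 points with 40 per arm and 11-14 points with 100 per arm.

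**4. Power for a 20-point fall in the NEC share.** Power = Φ{[0.20√n − 1.96√(2p̄(1 − p̄))] / √(p₁(1 − p₁) + p₂(1 − p₂))}, where p̄ is the mean of p₁ and p₂. AXR-arm shares of 30% to 60% are assumed.
- 67 in total (n = 33.5), 60% to 40%: (1.158 − 1.386)/0.693 = −0.33, power 37%.
- 81 in total (n = 40.5), 30% to 10%: (1.273 − 1.109)/0.548 = 0.30, power 62%.
- 200 in total (n = 100): 81% (60% to 40%) to 95% (30% to 10%).

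Steps 3 and 4 treat infants as independent. Allocation is by calendar month of birth (10.2), so true precision may be lower.

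**5. Could labelling matter for the durations?** This is an illustration; neither input is in the documents. If NEC-labelled infants take 10 to 12 days longer to reach full feeds and labelling differs by 10 to 20 points, labelling alone moves the arm means by 0.10 × 10 = 1.0 day to 0.20 × 12 = 2.4 days. The plan aims to detect 5 to 6 days.

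**The case against.** Several points on the other side are sound.

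- **The durations stand.** A reader might infer that they cannot be interpreted without diagnosis by arm. That does not follow. The trial compares imaging strategies, and the intention-to-treat difference estimates the total effect of the strategy by whatever route. Relabelling infants and feeding them sooner may be one way BUS works. Only the explanation is lost.
- **The hypothesis is not wholly untested.** The protocol measures change in diagnostic thinking, and each AXR + BUS infant is rated before and after BUS. That is a legitimate design for the question, though not a randomised one.
- **A by-arm NEC share should not replace the paired analysis.** The share shows only net change. If BUS rules NEC in for some infants and out for others, the shares can match while many diagnoses changed. Paired data can show those changes.
- **The label is not accuracy.** Section 26.1 says clinical diagnosis and gives no criteria, time point or adjudication. It should not be read as a final or verified diagnosis. Under 10.3 the care team sees the imaging, so in one arm the label is made knowing the BUS result. A difference would show changed labelling and could not by itself establish the favourable change in 2.2.
- **Precision is modest**, and the sizes above rest on assumed shares.

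These points limit what the added comparison can claim. They do not supply the missing randomised evidence.

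**Conclusion.** The point holds in limited form. Aim 1 makes a claim about diagnosis and a diagnosis variable is collected without restriction to one arm, but the only planned analysis of diagnosis is uncontrolled. The planned duration comparisons and the paired survey analysis are both worth keeping. The loss is a randomised estimate of how often infants are diagnosed with NEC under each strategy, and with it the ability to say whether a difference in durations goes with a difference in diagnosis.

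The added estimate would have a 95% CI half-width of about 18-22 points at the 80-infant target and 11-14 points at the 200-infant goal. This assumes an NEC share of 20-50%, 1:1 allocation and no clustering. At 67 to 81 in total it would have only about 37-62% power for a 20-point shift, so it should be reported as an estimate with its interval and not as a powered test. This is a cheap improvement; it does not invalidate any planned analysis.

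**What to change.** Add to 28.1, before any results are seen by arm, wording such as:

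*Secondary outcome: the proportion of infants with a clinical diagnosis of NEC (versus any other category in 26.1) for the first episode of NEC concern, as recorded by the treating team at [stated time point], will be compared between randomised arms by intention-to-treat, regardless of cross-over. It will be reported as a risk difference with a 95% CI that accounts for allocation by birth month and for site. The five diagnosis categories will be tabulated by arm.*

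Three details must be written out, because the documents do not contain them:
- the time point of the diagnosis, and that it is tied to the first episode (26.1 does not say whether diagnosis is recorded per episode or per infant);
- the method for birth month and site, since 28.1 specifies none for any outcome. One option is a regression for the risk difference with site as a covariate and standard errors clustered by birth month, with a small-sample correction;
- how infants without a recorded diagnosis are counted.

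Keep the paired survey analysis as the measure of diagnostic thinking. Report it beside the by-arm estimate and describe it as uncontrolled. State that the by-arm estimate reflects labelling, not accuracy, and is imprecise.

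Cost: a few sentences in 28.1 and a data-definition line for diagnosis, with no new assessments. The downside is one more secondary estimate with a wide interval. The comparison of days to full feeds is unaffected.

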10.6 Follow-up imaging

Infants with suspected NEC may need additional follow-up imaging for ongoing concerns of NEC. If the treating neonatologist deems follow-up imaging is needed, study infants will continue to have either AXR or AXR + BUS performed as determined by their randomization arm.

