32.0 Setting & Locations*

32.1 The NICU at CMKC is an 87-bed level IV NICU. Majority of infants admitted at the NICU are born at other hospitals and are typically transferred to CMKC due to need for specialized care. Neonatologists are in-house 24/7. As a children's hospital, radiology staff at CMKC are composed of pediatric sonographers and pediatric radiologists. BUS for NEC evaluation has been available at CMKC since 2015. Despite its availability, current use of BUS for NEC evaluation at CMKC remains highly variable, often dependent upon the individual preferences of the treating neonatologist.

32.2 The NICU at KUMC is a 32-bed level III NICU. Majority of infants admitted at the NICU are born at KUMC. Neonatology coverage at KUMC is provided by CMKC neonatologists who are also in-house 24/7. As a general adult hospital, radiology staff at KUMC are composed primarily of adult sonographers and adult radiologists. Currently, only one radiologist at KUMC has the expertise to perform BUS for NEC evaluation. Because of this limited availability, BUS for NEC evaluation is infrequently performed at KUMC. However, as part of our study's aim of investigating

generalizability of BUS in NICUs of adult hospitals, pre-study training will be done to standardize performance and availability of BUS between CMKC and KUMC.

32.3 Close research collaboration exists between the NICUs of CMKC and KUMC. Several research protocols done at CMKC are also done at KUMC. In fact, KUMC is such an active site for collaborative research that a CMKC-employed neonatology research coordinator ([name]) is dedicated solely for recruitment of participants at KUMC-NICU. Although KUMC has its own IRB, majority of the research done at KUMC NICU is approved via reliance on the IRB at CMKC.

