
The research could not practicably be carried out without the requested waiver/alteration (i.e., explain why the study could not be done if permission/assent/consent were required)
	
We initially conducted a pilot study to determine the feasibility of a RCT study design of BUS for NEC evaluation. While the RCT study design itself was feasible, we found that the process of obtaining consent was not practicable. The reasons why the proposed research could not be practicably carried out without the requested waiver are detailed below and in Fig 3:
 
(1) NEC is an emergency, making traditional parental consent at time of NEC concern impossible. Because NEC can rapidly deteriorate, infants with suspected NEC require “stat” evaluation with imaging and other laboratory tests. Families approached for research during emergency situations are often unable to give proper informed consent because of physical and emotional distress. Obtaining consent at time of NEC concern would also increase the risk of delaying evaluation. For these reasons, traditional parental informed consent at time of NEC concern is not possible for our study.
 
(2) Obtaining consent prior to NEC concern will require impractically large numbers to meet sample size demands. To overcome the emergency nature of NEC, we elected in our pilot study to seek consent from all infants who meet eligibility criteria, follow consented infants over time, and randomize only consented infants who develop concern for NEC. The problem with this approach is that only 36% (20/56) of consented infants developed NEC concern for randomization into the study. Based on these numbers, we will need to successfully consent 222 infants to achieve our target sample size of 80 infants. Although mathematically possible, it would require implausibly high approach and consent rates to successfully enroll 222 infants over the 2 years of the proposed study, making this approach of obtaining consent prior to NEC concern impracticable. This approach would also intrude on many families who would not need and may not

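### Aim 2 hypothesises that BUS is comparable between the two NICUs, but the planned difference tests and a kappa with no site comparison cannot support that conclusion

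*Combined protocol and SAP*

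**What the plan says.** The study summary (section 1.0) gives the Aim 2 hypothesis: "We hypothesize that BUS timeliness, quality, and inter-rater reliability are comparable between level III and IV NICUs". It has three components: timeliness, quality and reliability.

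Section 28.2 gives one sentence to each:

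- Timeliness: "We will use t-test to analyze differences in mean time of BUS image acquisition and reporting".
- Quality: "Chi-square test will be used to compare differences in proportion of BUS studies that were performed and reported per standardized protocol".
- Reliability: "Inter-rater reliability for BUS studies will be assessed by" Cohen's kappa.

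Section 28.2 does not name the groups compared. It gives no confidence interval, no margin or other criterion for comparability, no expected number of BUS studies, and no kappa by site. The sample size in section 28.3 rests only on duration to full feeds, which is an Aim 1 outcome.

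On the volume of data, section 28.3 speaks of "For a 1-year study with 67 to 81 distinct episodes", Addendum B of a target of 80 infants and of a two-year study ("to successfully enroll 222 infants over the 2 years of the proposed study"), and section 8.0 of 200 neonates, 120 at CMKC and 80 at KUMC. Follow-up imaging repeats BUS in the same infant (section 10.6: "study infants will continue to have either AXR or AXR + BUS performed as determined by their randomization arm"), and 28.2 does not say whether those repeat scans are analysed.

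**The concern.** A t-test and a chi-square test take no difference as the null hypothesis. A small P value contradicts comparability. A large one shows only that a difference was not detected, which is the expected result of a small sample whether or not the sites differ. A kappa that is not compared between sites does not address whether reliability is similar at both. So none of the three components of the hypothesis has a planned analysis that could support it. The plan does not say that P > 0.05 will be read as comparable, but it offers no other route to that conclusion.

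This matters because section 32.2 makes it an aim of the study to investigate "generalizability of BUS in NICUs of adult hospitals, pre-study training will be done" to bring the two sites to a common standard. The same section says that KUMC currently has one radiologist with the expertise, so a real gap is plausible despite the training. As written, Aim 2 could end with a non-significant test and no statement of how large a gap the data still allow.

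**Working it through.** **1. The plan's own sample size.** Table 1 in section 28.3 follows from N = 4 × [SD × (1.96 + 0.8416) / d]². For SD 8 and d = 5 days, 4 × (8 × 2.8016 / 5)² = 80.4, stated as 81. For d = 6 days the result is 55.8, stated as 56. The other cells also reproduce, allowing for rounding up within each group. The table is sound for its purpose, but no equivalent exists for Aim 2.

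**2. Number of BUS studies by site.** The documents give no count. Assume 1:1 arms, the 120:80 (60:40) site split of section 8.0, and one scan per episode in the AXR + BUS arm. Then CMKC has episodes × 0.5 × 0.6 scans and KUMC has episodes × 0.5 × 0.4.

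- (a) One year, 67 to 81 episodes (81 is close to Addendum B's target of 80 infants): 20 vs 13 to 24 vs 16.
- (b) Two years at that rate, 134 to 162 episodes: 40 vs 27 to 49 vs 32.
- (c) All 200 infants of section 8.0 randomised: 60 vs 40.

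**3. What the data could show.** The methods are:

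- Chance that the chi-square test misses a true gap: 1 − power, by exact enumeration of the uncorrected test at two-sided 0.05. The true rates of 90% vs 70% and 90% vs 60% are assumed.
- 95% CI half-width for a difference in proportions, 90% assumed at both sites: 1.96 × √[0.09 × (1/n₁ + 1/n₂)].
- 95% CI half-width for a difference in mean times, in SD units: t(0.975; n₁ + n₂ − 2) × √(1/n₁ + 1/n₂).
- 95% CI half-width for kappa at KUMC, assuming kappa 0.7, 50% prevalence and two raters: 1.96 × √[(1 − 0.49)/n₂].

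| Scans, CMKC vs KUMC | Miss 90% vs 70% | Miss 90% vs 60% | Half-width, proportion | Half-width, mean time (SD) | Half-width, KUMC kappa |
|---|---|---|---|---|---|
| 20 vs 13 | 66% | 44% | 21 points | 0.73 | 0.39 |
| 24 vs 16 | 67% | 41% | 19 points | 0.65 | 0.35 |
| 40 vs 27 | 42% | 15% | 15 points | 0.50 | 0.27 |
| 49 vs 32 | 36% | 10% | 13 points | 0.45 | 0.25 |
| 60 vs 40 | 25% | 5% | 12 points | 0.41 | 0.22 |

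**4. Repeat scans.** Two scans per episode with within-episode correlation ρ count as 2/(1 + ρ) independent scans: 1.54 at ρ = 0.3 and 1.33 at ρ = 0.5 (both assumed). They help, but by less than their number.

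**5. What a formal claim would need.** For non-inferiority on the per-protocol proportion (90% at both sites, one-sided 2.5%, 80% power, 60:40 split), total N = (1.96 + 0.8416)² × 0.09 × (1/0.6 + 1/0.4) / margin². This gives about 131 scans for a 15-point margin and 295 for 10 points. These margins are illustrations; the documents give none.

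**The case against.** The strongest reply is that *comparable* was never meant as a formal equivalence claim. The objective of Aim 2 is to determine the capability of implementing BUS. Section 2.1 restates that without the word, and the hypothesis in section 2.2 does not mention timeliness, quality or reliability. Mean times, per-protocol proportions and kappa are then descriptive evidence of capability. This has force. But section 1.0 does state the hypothesis, and if the intent is descriptive, the analysis that fits is estimates with intervals, not significance tests.

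Several smaller points stand. The groups can be inferred: BUS is done almost only in one arm, so 28.2 must be comparing sites, and naming them is a clarification. The raters are not defined. If a reader at one site re-reads the other site's scans, kappa is itself a measure of cross-site agreement, so the kappa half-widths above hold only for two raters assessing KUMC scans. The scan counts and true rates are assumed, and the miss rate for 90% vs 70% ranges from 25% to 67%. With 13 to 16 scans at KUMC and a 90% rate, one or two failures are expected, so the simple interval for a proportion is only a rough guide. In the best case, 200 infants with two scans each, 100 scans per protocol arm would become about 133 to 154 effective scans, enough for a 15-point margin. That case is favourable on every count and the plan does not commit to it.

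None of this gives the planned tests the power to support comparability.

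**Conclusion.** The concern holds. Section 28.2 can contradict the Aim 2 hypothesis but cannot support it, and this follows from the tests chosen, whatever the sample size.

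The size of the consequence depends on scan counts that the plan does not give. On the assumptions above, a 20-point gap in per-protocol scans would be missed between a quarter and two thirds of the time. With 90% at both sites, the interval for the difference would extend 12 to 21 points either side of the estimate. The analysis and wording of Aim 2 should be changed; Aim 1 outcomes are unaffected.

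**What to change.** In section 28.2:

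- Name the comparison as KUMC minus CMKC.
- Make the primary Aim 2 analysis the site difference with 95% CI for time to acquisition, time to report and proportion per protocol. With few failures expected at KUMC, use an interval method for the proportion suited to small counts.
- Say who the raters are, and report kappa by site with 95% CI.
- Say whether the index scan or all scans are analysed. If all, allow for repeat scans in the same infant.
- State that a non-significant test will not be read as comparability.

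In section 1.0, reword the Aim 2 hypothesis as estimation of the site differences. Keep *comparable* only if a margin is fixed before data are seen and the claim is made only when the CI excludes it.

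The cost is a few sentences and no new data. The downside is that, at the planned size, Aim 2 will probably yield an estimate of the site gap and not a claim of comparability.

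### Aim 2 states its hypothesis for level III versus level IV NICUs, but with one site per level the planned tests can only compare KUMC with CMKC

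*Combined protocol and SAP*

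**What the plan says.** Section 1.0 sets out the design: "We propose to conduct this study in two diverse sites". It continues: "The first site will be the level IV NICU of Children's Mercy Kansas City (CMKC), which already has expertise in BUS for NEC". KUMC, the other site, is a level III NICU in an adult hospital with less BUS experience.

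The Aim 2 objective in 2.1 is singular: "Determine the capability of implementing BUS for NEC evaluation in a level III NICU within an adult hospital". The hypothesis attached to that aim in 1.0 is about classes of NICU: "We hypothesize that BUS timeliness, quality, and inter-rater reliability are comparable between level III and IV NICUs". The general hypothesis in 2.2 also extends the expected benefit to less specialized centers.

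Section 28.2 gives the Aim 2 analysis. For timeliness: "We will use t-test to analyze differences in mean time of BUS image acquisition and reporting". For quality: "Chi-square test will be used to compare differences in proportion of BUS studies that were performed and reported per standardized protocol". Reliability is to be assessed by Cohen's kappa, with no between-site comparison described. There is no term for infant, operator or site, no margin for comparability, and no statement limiting the conclusion to the two hospitals.

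Section 32.2 adds two relevant facts. On staffing: "Currently, only one radiologist at KUMC has the expertise to perform BUS for NEC evaluation". On purpose and preparation, it ties the study to "generalizability of BUS in NICUs of adult hospitals, pre-study training will be done to standardize performance", and the sentence goes on to cover availability at the two named sites. Sections 10.6 and 10.7 allow follow-up imaging and repeat episodes, so one infant can contribute several BUS studies.

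**The concern.** NICU level is a property of the hospital. Here it coincides with hospital type, radiology staffing and prior BUS experience, and with everything else that differs between KUMC and CMKC. A test on individual BUS studies can show whether these two NICUs differed. It carries no information on how much two hospitals of the same level differ from each other, which is what a statement about level needs.

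The problem runs in both directions. A significant result could be reported as a level III versus level IV difference when it reflects one hospital or a few operators. A non-significant result could be reported as evidence that BUS transfers to level III NICUs. The second matters more, because the hypothesis is comparability and the study is meant to inform wider adoption. In addition, a non-significant t-test or chi-square test with no margin does not show comparability even for the two sites.

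**Working it through.** **Is there a planned figure to reproduce?** Not for Aim 2. Section 28.3 sizes only days to full feeds (Aim 1). Its Table 1 reproduces as total N: for a 5-day difference and SD 8, 4 × (8 × (1.960 + 0.842) / 5)² = 80.4, rounded up to 81 as printed. That has no bearing on Aim 2, which has no sample size, margin or ICC.

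**Can level be separated from site?** Between-site variation within level has (1 − 1) + (1 − 1) = 0 degrees of freedom. No analysis of these data can estimate it, so none can test level. This needs no assumption.

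**Illustration of a false difference in level.** Inputs:
- Site goals of 120 and 80 infants (8.0), a 60:40 split.
- The 80-infant target in Addendum B, which at 60:40 is 48 + 32.
- Assumed: half of the infants have BUS and each has one study, giving 60 + 40 or 24 + 16 studies.
- Assumed: a site ICC ρ, the share of variance due to hospitals of the same level differing, and no true effect of level.

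The test uses V_test = (1 − ρ)(1/n₁ + 1/n₂). For a claim about level the true variance is V_true = 2ρ + V_test. The false-positive rate is 2 × [1 − Φ(1.96 × √(V_test / V_true))].

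Example, 60 + 40 and ρ = 0.05: 1/60 + 1/40 = 0.04167; V_test = 0.95 × 0.04167 = 0.0396; V_true = 0.10 + 0.0396 = 0.1396; 1.96 × √(0.0396 / 0.1396) = 1.04; rate 29.7%.

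| Site ICC (assumed) | 24 + 16 studies | 60 + 40 studies |
|---|---|---|
| 0 | 5.0% | 5.0% |
| 0.01 | 7.3% | 10.8% |
| 0.02 | 9.7% | 16.4% |
| 0.05 | 16.7% | 29.7% |
| 0.10 | 26.8% | 43.6% |

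More infants at the same two sites raise the rate, because V_test shrinks while 2ρ does not.

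**The comparability direction, for the two sites only.** With independent studies, the 95% CI for a mean difference has half-width 1.96 × √(1/n₁ + 1/n₂) in SD units: 0.40 SD for 60 + 40 and 0.63 SD for 24 + 16. Even an observed difference of exactly zero leaves true site differences of that size inside the interval.

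**Repeat studies in an infant.** The design effect is 1 + (m − 1) × ICC. Assuming m = 2 to 4 studies per infant and a within-infant ICC of 0.1 to 0.5, it runs from 1.1 to 2.5. A nominal 5% test of the two sites then has an error rate of about 6% to 21%, and a correct CI is wider by √1.1 to √2.5, that is 5% to 58%.

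**Operators.** Replace 2ρ by ρ(1/k₁ + 1/k₂), where k₁ and k₂ are the numbers of readers. With 60 + 40 studies and an assumed operator ICC of 0.05, 6 readers at CMKC and 1 at KUMC give 21.3%; 10 and 3 give 11.5%. This applies only if the site result is meant to extend beyond the operators who took part. The reader counts are assumed.

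**The case against.** The strongest reply is that Aim 2 is a single-site capability aim. The objective speaks of one level III NICU, 1.0 names both sites, and 28.2 draws no conclusion about level and does not name the groups compared. On that reading, one loosely worded hypothesis is being held against a sensible two-hospital comparison. Much of this stands: the over-reach is in the hypothesis sentence and the generalizability language of 2.2 and 32.2, not in the objective. It does not remove the point, because the hypothesis is what 28.2 is there to address and nothing limits it to these hospitals.

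Three stronger readings are tempting and are not supported.
- A reader might infer that the planned tests are invalid. With one BUS per infant they are valid for KUMC versus CMKC with the operators who took part.
- A reader might infer that Aim 2 has a false-positive rate of 17% or 30%. Those figures rest wholly on an assumed ICC, and they measure a false difference, whereas the hypothesis is comparability.
- A reader might infer that the KUMC result will be one reader's result. Section 32.2 describes the position before the study, speaks of expertise to perform BUS, and commits to pre-study training that may add operators.

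Training and shared neonatologist cover may also narrow the gap between the sites. Neither separates site from level.

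**Conclusion.** The point holds for the scope of the Aim 2 claim. With one site per level, the 28.2 tests compare KUMC with CMKC, and no result from them, significant or not, supports a conclusion about level III versus level IV NICUs. This follows from the design alone.

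Its numerical size is not known from the documents. Under assumed site ICCs of 0.01 to 0.10, one BUS per infant and half of infants imaged by BUS, the illustrative rate of a false level difference is about 7% to 27% (24 + 16) or 11% to 44% (60 + 40). Two related gaps are smaller and can be repaired: repeat studies in one infant are not allowed for, and the operator is not among the data items in 26.1. Aim 1 is not affected. The matter should be corrected before analysis because it changes what Aim 2 may conclude, but it does not undermine the two-site comparison itself.

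**What to change.** 1. Reword the Aim 2 hypothesis to match the singular objective: BUS timeliness, quality and reliability at KUMC compared with CMKC.
2. In 28.2, name the two sites as the groups. Report site-specific estimates for each measure, including kappa by site, and the site difference with a 95% CI that allows for repeat BUS studies in the same infant, for example cluster-robust by infant or restricted to the first BUS per infant.
3. State that a non-significant P value will not be read as comparability, that the P values do not test NICU level, and that extension to other level III NICUs is descriptive.
4. Add the performing sonographer and reading radiologist (coded) to the BUS items in 26.1, collected at chart review. Report times and protocol adherence by operator within site. If a site has only one reader after training, state that site and reader cannot be separated. The infant-clustered CI does not cover variation between operators, so describe it as applying to the operators who took part.

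The cost is protocol and SAP wording and two chart-review fields, with no added infants, sites or procedures. The downside is a narrower Aim 2 claim and a somewhat wider CI where infants contribute several studies.
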